7.6.2 EQ-5D-5L

The EQ-5D-5L is described in Section 9.4.1; subjects complete the EQ-5D-5L at baseline and Week 24/ET. For each of the 5 dimensions, the number and percentage of subjects in each of the 5 levels will be summarized within each active treatment group and placebo in a '5x5' contingency table representing baseline versus Week 24/ET. Only subjects who have completed the EQ-5D-5L at both baseline and Week 24/ET and have complete data for each dimension will be included in the summary.

For the EQ-5D-5L Visual Analogue Scale (VAS), the change from baseline to Week 24/ET VAS will be analyzed using the ANCOVA model described in Section 7.1.5. The model-based LS mean difference between each active treatment group and placebo (active-placebo), 95% CI, and nominal p-value will be displayed. A worst VAS score of '0' will be assigned for the composite strategy, per the primary estimand.

7.6.3 Health and Performance Questionnaire (HPQ)

The World Health Organization (WHO) Health and Performance Questionnaire (HPQ) is a work productivity questionnaire which asks about employment status, work absences, and on-the-job productivity. The HPQ is measured at baseline, and at weeks 4, 8, 12, and 24/ET. HPQ variables will be defined and summarized outside of this analysis plan.

7.6.4 SF-6D

The SF-6D provides a means for using the SF-36 in economic evaluation by estimating a preference-based single index measure for health from these data using general population values. The SF-6D can be used to obtain quality adjusted life years (QALYs) from the SF-36 for use in cost utility analysis. SF-6D will be scored and summarized outside of this analysis plan.

7.7 Per Protocol Analysis

As a sensitivity analysis, the co-primary endpoints will be analyzed using the Per Protocol Set, defined in Section 5.6, according to the primary estimand and estimation methods used in the primary analyses and described in Sections 7.1.1–7.1.5.

7.8 Subgroup Analyses

The following endpoints will be analyzed according to the primary estimand for the following stratification subgroups:

1. Subjects with versus without polyps at baseline
2. Subjects with versus without prior sinus surgery at baseline

These subgroups are defined based on a subject's actual polyp status and actual nasal surgery status at baseline.

7.8.1 Subgroup Analysis of Co-Primary Endpoints

- a) Change from baseline to the end of Week 4 in the 7-day average AM, instantaneous CSNS
- b) Change from baseline to Week 24/ET in the APOV in the ethmoid and maxillary sinuses.

7.8.2 Subgroup Analysis of Daily Nasal Symptom Scores

- a) Changes from baseline to Weeks 4, 8 and 12 in the 7-day average of AM, PM, and instantaneous, reflective individual nasal symptoms scores (16 endpoints at each time point: four individual nasal symptom scores each at four endpoints).
- b) Changes from baseline to Weeks 4, 8 and 12 in the 7-day average of AM, PM, and instantaneous, reflective CSNS scores (4 endpoints at each time point) – except primary endpoint covered above.

7.8.3 Subgroup Analysis of SNOT-22 Total and Domain Scores

- a) Changes from baseline to Weeks 4, 8, 12 and 24/ET in SNOT-22 total scores and each of the 5 Domain scores.

7.8.4 Subgroup Analysis of APOV in Individual Sinuses

- a) change from baseline to Week 24/ET in APOV-E
- b) change from baseline to Week 24/ET in APOV-M

7.8.5 Subgroup Analysis of POV in the Worst Sinus

- c) change from baseline to Week 24/ET in WPOV
- d) change from baseline to Week 24/ET in WPOV-E
- e) change from baseline to Week 24/ET in WPOV-M
- f) change from baseline to Week 24/ET in WZLM

7.8.6 Models for Subgroup Analyses

The primary estimand and models described in described in Sections [7.1.3-7.1.5](#) will also include the appropriate terms for treatment-by-subgroup interaction as well as the appropriate contrasts to obtain the within-subgroup inferential statistics. The model-based, within-subgroup LS mean difference between each active treatment group and placebo (active-placebo), 95% CI, and nominal p-value will be displayed, as well as the treatment-by-subgroup interaction nominal p-value.

For the APOV endpoint, the subgroup analysis will be based on the same MI dataset created for the primary analysis.

8 SAFETY ANALYSIS

The Safety Analysis Set defined in Section 5.4 will be used for all safety analyses specified in this section unless otherwise noted. Safety and tolerability will be assessed by clinical review of all relevant parameters including adverse events, laboratory tests, and physical and vital sign measurements.

All safety summaries will be descriptive and will be displayed by treatment group in the following order (left to right): Placebo, OPN-375 186 µg, OPN-375 372 µg, and OPN-375 combined doses.

8.1 Study Drug Exposure and Administration

Study drug exposure will be measured by study duration which is defined in Section 9.1.1. Summary statistics for the duration of drug exposure will be calculated and presented using the Kaplan-Meier method which will display in a figure the proportion of subjects with continuing drug exposure over the duration of the study, by treatment group. A corresponding table will include the summary statistics for duration of exposure, including minimum, maximum, and quartiles, median duration and 95% confidence interval for the median duration.

Compliance is calculated as follows.

$$\text{Compliance} = \frac{\text{number of doses of study medication}}{\text{Study Duration} \cdot 4} \cdot 100$$

8.2 Adverse Events

All adverse events will be coded using the Medical Dictionary for Regulatory Activities (MedDRA) Version 21.0 or greater. Treatment emergent adverse events (TEAEs) are defined as adverse events with onset dates on or after the first dose of DB study drug. Further details regarding the definition of TEAEs are provided in Section 9.5.2.

All AE summaries will include total number of TEAEs and total number of subjects with TEAEs unless otherwise stated. The incidence of adverse events will be summarized using descriptive statistics by system organ class and preferred term. Subjects are counted only once in each system organ class category, and only once in each preferred term category. For the summaries by severity, subjects are counted at the greatest severity and will not have the number of events included. Additional summaries by severity will provide all adverse events for overall TEAEs and treatment related TEAEs.

An overall summary of adverse events will include number (%) of subjects with TEAEs (and number of AEs), treatment-related TEAEs, SAEs, severe TEAEs, TEAEs that resulted in treatment discontinuation, and fatal AEs; this overall AE summary will be presented for the Safety Analysis set.

Additionally, summaries will be presented for all TEAEs by system organ class and preferred term (overall and by severity). TEAEs determined by the investigator to be treatment-related (overall and by severity) will be summarized. Serious AEs will also be summarized. TEAEs causing permanent discontinuation from treatment will be summarized, and AEs resulting in death will be summarized.

A summary of adverse events that started during the placebo run-in period will be presented for both Safety Analysis set and the Enrolled Subjects set.

Listings for pre-treatment AEs, fatal AEs, serious AEs, and TEAEs leading to discontinuation will also be presented.

8.3 Clinical Laboratory Tests

Blood and urine samples will be collected at Screening (Visit 1) only. Screening laboratory values will be provided in the listings. No summary statistics will be created.

8.4 Urine Pregnancy Test

For women of childbearing potential, urine pregnancy tests will be performed at the site during every visit. Urine pregnancy test results will be provided in a listing.

8.5 Nasal Examinations

The nasal examination will be performed during the placebo run-in period and again at the Week 24/ET visit. The nasal examination will be performed via nasoendoscopy. Sites will be provided with a nasal examination worksheet and a polyp grading sheet. At the nasal examination, the subject is evaluated for epistaxis and non-active bleeding, septal erosion/ulceration/perforation, ulcerations in areas of the nose other than septum, and mucosal candidiasis. A summary of the key safety assessments from the nasal examination is provided in the Protocol, Attachment 3.

Findings of the nasal examination will be collected on the nasal examination CRF. Findings from the nasal examination worksheet that are deemed to be clinically significant by the Investigator will also be recorded on the AE CRF. The nasal examination findings will be summarized with descriptive statistics.

8.6 Ocular Examinations

An ocular examination is an unscheduled visit and must promptly be performed if a subject experiences any unexplained worsening in vision during the study (e.g. difficulty reading or seeing traffic signs from a distance). The examiner must be a health care provider with expertise in examination and diagnosis of conditions of the eye. Reports will be forwarded to the investigator.

Results of Ocular Examinations will be presented in the Subject Listings.

8.7 Vital Signs

Vitals signs at each visit and changes from baseline to each visit will be summarized using descriptive statistics.

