### **9.9.1 Adverse Events (AEs)**

All reported AEs will be coded using the Medical Dictionary for Regulatory Activities (MedDRA) version 20 or higher. Treatment-emergent AEs (TEAEs) are defined as AEs with onset dates on or after the start of double-blind study drug. The incidence of TEAEs during the study period will be tabulated by treatment group and body system (or System Organ Class [SOC] and preferred term) overall, by severity, and by relationship to study drug using subject counts and percent. Those AEs with missing onset dates or missing severity will be included as treatment-emergent. If an AE is reported more than once during the double-blind study phase, the greatest severity and the worst-case attribution will be used for presentation in tables.

Deaths, SAEs, and AEs causing discontinuation of study participation and /or study treatment will be tabulated by treatment group with subject counts and percent. Adverse events for individual subjects will be listed, along with information regarding onset, duration, severity, and relationship to study drug.

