### **9.9.2 Other Safety Endpoints**

Baseline physical examination findings and clinical laboratory data will be summarized. Vital signs and weight will be summarized using descriptive statistics including mean values and change from baseline values, as well as numbers of subjects with values outside limits of the normal range at each time point.

Prior/concomitant medications will be coded using the World Health Organization (WHO) Drug Dictionary (WHODrug), Version December 2010 or later, and summarized by drug class with subject counts and percent.

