2 INTRODUCTION

This Statistical Analysis Plan (SAP) has been developed after review of Sponsor Protocol OPN-FLU-CS-3205 (Amendment 6.0, dated 07 January 2022) and the corresponding electronic case report form (eCRF). This SAP describes the statistical methods to be used for the analysis and reporting of all efficacy and safety data collected during the conduct of Protocol OPN-FLU-CS-3205.

This SAP supersedes the statistical considerations identified in original Protocol OPN-FLU-CS-3205, as well as the SAP dated 19 April 2021, which is based on Protocol Amendment 4.1 and is the basis for the IASAP dated 8 June 2021. This SAP contains all changes incorporated into Protocol Amendment 6.0, and there are no deviations from this amendment presented in this SAP. If additional analyses are performed to supplement the planned analyses described in this SAP they will be identified as such in the Clinical Study Report (CSR).

This SAP is being written with consideration of the recommendations outlined in the following International Conference on Harmonization (ICH) Guidance for Industry documents:

- E9: Statistical Principles for Clinical Trials
- E9-R1 Addendum: Estimands and Sensitivity Analysis
- ICH E3: Structure and Content of Clinical Study Reports

This SAP also incorporates the recent FDA Guidance regarding the COVID-19 Public Health Emergency (PHE):

- FDA Guidance on the Conduct of Clinical Trials of Medical Products during COVID-19 Public Health Emergency: Guidance for Industry, Investigators, and Institutional Review Boards, (11 May 2020)

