3.4.4 Safety Endpoints

Safety Endpoints include:

- Prior-concomitant and concomitant medications
- Vital signs and weight
- Nasal and endoscopic assessments
- Nasal examinations
- Adverse Events

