6 STUDY POPULATION SUMMARY

All study population summaries will be based on the Safety Analysis Set, (reference Section 5.4), and summarized by treatment group and total population, unless otherwise indicated.

Descriptive statistics for continuous variables include n, mean, standard deviation (SD), standard error (SE) of the mean, median, minimum, and maximum. Descriptive statistics for categorical variables include subject counts and percentages. Percentages are based on the number of subjects in the analysis set for whom there are non-missing data at the specified visit, unless otherwise specified. Counts of “missing” will be presented if at least one treatment group has missing data.

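### The SAP omits the protocol's out-of-range counts for vital signs and weight, gives weight no on-treatment summary, and narrows the AE-discontinuation table, none of it disclosed

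*SAP*

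**What the plan says.** **Vital signs and weight.** Protocol 9.9.2 has two parts. The first is "Vital signs and weight will be summarized using descriptive statistics including mean values and change from baseline values". The second follows directly: "as well as numbers of subjects with values outside limits of the normal range at each time point". SAP 8.7 consists of one sentence: "Vitals signs at each visit and changes from baseline to each visit will be summarized using descriptive statistics". SAP 3.4.4 nevertheless lists "Vital signs and weight" among the safety endpoints, and the schedule in SAP 3.2 has both measured at every clinic visit.

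**AEs and discontinuation.** Protocol 9.9.1 states that "AEs causing discontinuation of study participation and /or study treatment will be tabulated by treatment group", as subject counts and percentages. SAP 8.2 states that "TEAEs causing permanent discontinuation from treatment will be summarized". It adds a listing of TEAEs leading to discontinuation.

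**Disclosure.** SAP 2 asserts that "there are no deviations from this amendment presented in this SAP". SAP 11 itemises changes made after Amendment 6.0; all of them concern efficacy objectives, endpoints, definitions or sensitivity analyses.

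**The concern.** The protocol made specific commitments on safety tables, and the SAP, which governs what is programmed, delivers less without saying so. A reader who relies on SAP 2 and SAP 11 would conclude that the protocol's safety outputs are intact.

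Three things would be missing from the report:

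- how many subjects in each arm had blood pressure or pulse outside normal limits at each visit;
- any on-treatment summary of weight;
- a table by arm of AEs that led subjects to leave the study, as distinct from stopping the drug.

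The last distinction matters in this trial. Protocol 4.3 encourages subjects who stop treatment to stay in the study, and it gives an adverse event as a possible reason for withdrawal from the study itself.

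**Working it through.** The plan states no figure on this point, so there is none to reproduce. The check is a comparison of the texts, followed by a short illustration of what the missing counts would and would not add.

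**Side by side**

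| Item | Protocol | SAP |
|---|---|---|
| Vital signs: values and change | 9.9.2: yes | 8.7: yes |
| Vital signs: out-of-range counts by visit | 9.9.2: yes | 8.7: absent |
| Weight: values and change | 9.9.2: yes | Section 8: absent |
| Weight: out-of-range counts | 9.9.2: yes, limits undefined | Absent |
| AEs ending treatment, by arm | 9.9.1: yes | 8.2: yes |
| AEs ending study participation, by arm | 9.9.1: yes | 8.2: no table |
| Change disclosed | n/a | Not in SAP 11; denied in SAP 2 |

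**Does SAP 8.7 cover weight by implication?** Not on the SAP's own usage. SAP 3.3.4 explains vital signs as blood pressure and pulse and lists weight separately; Protocol 7.4.4 draws the same line. The only weight summary in the SAP is in the demographics (6.2). Weight is therefore an endpoint with four scheduled post-baseline assessments (Weeks 4, 8, 12 and 24/ET) and no analysis.

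**Is the SAP 2 sentence wrong only because of these items?** No. SAP 11 itself lists endpoints added and one endpoint removed after Amendment 6.0, so the sentence is inaccurate even on the SAP's own account. Protocol 9.9.2 also says that laboratory and physical examination data will be summarised, whereas SAP 8.3 and 8.8 provide listings only; SAP 11 does not mention that either.

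**Illustration, with assumed inputs.** The only document figure is n = 111 per arm. The SD of systolic change (10 to 14 mm Hg), the shift (30 mm Hg) and the share affected (5%) are assumptions.

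- Standard error of an arm difference = SD × √(2/111): 1.34 at SD 10, 1.61 at SD 12, 1.88 at SD 14.
- Shift in the arm mean = 0.05 × 30 = 1.5 mm Hg, which is 1.5/1.88 = 0.80 to 1.5/1.34 = 1.12 standard errors. The mean alone would not show it clearly.
- The spread does move. With 6 of 111 subjects shifted and SD 12, the variance is 144 + (6/111)(105/111)(900) = 144 + 46 = 190, so the SD rises from 12.0 to 13.8. The maximum would also rise.
- A count is not clearly more sensitive. Assume visit systolic pressure with mean 125 and SD 15, and an arbitrary cut of 140 used only for the arithmetic. The background is 111 × 0.159 = 17.6 subjects. The same 5% adds 111 × 0.05 × (0.841 − 0.159) = 3.8, giving 21.4. The standard error of the difference in proportions is √[(0.159 × 0.841 + 0.193 × 0.807)/111] = 0.051, so the contrast is (3.8/111)/0.051 = 0.67 standard errors.

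The illustration therefore does not show that the counts would detect a harm that the descriptive statistics would miss. They report something different: how many subjects in each arm were out of range. That is the quantity the protocol promised.

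**The case against.** The strongest reply is that these are small gaps in descriptive tables and that the SAP covers much of the ground elsewhere. Several parts of it stand.

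- A reader might infer that SAP 8.7 leaves nothing but means. The documents do not support that. SAP 6 says: "Descriptive statistics for continuous variables include n, mean, standard deviation (SD), standard error (SE) of the mean, median, minimum, and maximum". That definition sits under the study population summaries, so carrying it into Section 8 is a reasonable reading rather than an explicit rule. If it applies, the largest individual changes in blood pressure and pulse would appear.
- A reader might infer that systemic steroid effects would go unseen, or that blood pressure and weight are the only on-treatment measures able to show them. That does not follow. AEs are collected throughout and tabulated by class, term and severity, and unexplained visual worsening triggers an eye examination (Protocol 7.4.3, SAP 8.6). Neither document ties the vital-sign counts to steroid effects.
- A reader might infer that an AE that drives a subject out of the study after treatment has stopped is not tabulated at all. It is. SAP 9.5.2 defines TEAEs by onset on or after first dose with no end cut-off, and SAP 8.2 tabulates them all. What is lost is the classification by study discontinuation. The listing in SAP 8.2 and the disposition table in SAP 6.1 partly cover it, but neither is an AE table by arm.
- Protocol 9.9.2 gives no numerical limits, and a normal range for weight is undefined in both documents, so the counts cannot be programmed as they stand.

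None of this supplies the out-of-range counts, the weight summary or the disclosure.

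**Conclusion.** The mismatch is real and rests on the texts alone. Run as written, the SAP leaves a stated safety endpoint, weight, without any on-treatment analysis, omits the protocol's out-of-range counts, and narrows the AE-discontinuation table. It discloses none of these cuts, and its statement that nothing departs from Amendment 6.0 is incorrect.

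The size is modest. The effect is confined to descriptive safety reporting, which both documents present without inference, and the data remain available. No endpoint definition, efficacy estimate, alpha or sample size changes. Extreme blood pressure or pulse values may still be visible through the minimum and maximum, provided the SAP 6 definition applies to Section 8. The blood pressure illustration rests on assumed inputs and supports no claim that a particular harm would be missed. The AE-table gap is a separate reporting matter with no bearing on whether vital-sign shifts are seen.

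It should be corrected because the protocol promised these outputs and restoring them is cheap.

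**What to change.** 1. **SAP 8.7:** name weight alongside vital signs. Add the Protocol 9.9.2 counts of subjects outside normal limits by arm and visit. The sponsor should state the reference limits before unblinding; for weight, either state a criterion or record that the count does not apply. Cross-refer to the definition of descriptive statistics in SAP 6 so that minimum and maximum are explicit. Any-time-on-treatment or shift tables would go beyond the protocol's commitment and are not needed to close the gap.
2. **SAP 8.2:** extend the AE-discontinuation table to cover discontinuation of study participation as well as of treatment, by arm, with counts and percentages.
3. **If any of these is deliberately left out:** list it in SAP 11 with a reason.
4. **In either case:** correct the sentence in SAP 2, which SAP 11 already contradicts.

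The cost is SAP wording, an agreed set of limits and a few descriptive tables. No new data collection is required.

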8.8 Physical Examination

A brief physical examination will be performed on all subjects at Screening (Visit 1). Height will be collected. Results of the brief physical examination will be presented in the Subject Listings.

8.9 Concomitant Medications

Concomitant medications include all medications and other treatments taken by the subject during the study, including those treatments initiated prior to the start of the study. Specifically, concomitant medications are defined as non-study medications with a start date on or after the first dose of study medication inclusive. Medications that started prior to the first dose of study medication but continued during treatment will also be defined as concomitant. Further details regarding the definition of concomitant medications are provided in Section 9.5.1.

Concomitant medications will be coded using the World Health Organization (WHO) Drug Dictionary (WHODrug), Version December 2010 or later, and summarized descriptively by treatment group and drug class with subject counts.

Concomitant medications will be summarized by therapeutic class and preferred term for the Safety Analysis Dataset. For each subject, multiple records of the same concomitant medication will be counted only once within each therapeutic class and preferred term.

All concomitant medications will be provided in a listing for the placebo run-in period based on the Safety Analysis set and Enrolled Subjects set.

8.10 Rescue Medications

The incidence of rescue medication use during the placebo-run period will be presented in the Subject Listings.

